A randomized, open-label, multi-centre trial comparing hemodialysis plus hemoperfusion versus hemodialysis alone in adult patients with end-stage renal disease (HD/HPvsHD)

A randomized, open-label, multi-centre trial comparing hemodialysis plus hemoperfusion versus hemodialysis alone in adult patients with end-stage renal disease (HD/HPvsHD): study protocol

Trial registration numbers: ClinicalTrials.gov Identifier: NCT03227770

Date of the document: 04/14/2018

SPECIFIC AIMS AND HYPOTHESIS

The prevalence of end-stage renal disease (ESRD) is increasing with an enormous financial burden.^[1,2] About 50 years ago, ESRD was invariably lethal. Although maintenance dialysis have now successfully prolonged the life of ESRD patients, mortality remains high.^[3]

Approximately 9-13% of patients on hemodialysis in India die within 1 year.^[4] The adjusted rates of all-cause mortality are 6.3-8.2 times greater for dialysis patients than the general population.^[5] The adequacy of dialysis and factors such as pre-dialysis care, late referral to nephrology specialists and non-compliance greatly affect patient's survival.

The gold standard of hemodialysis therapy is yet to be identified. New approaches are required to improve overall mortality rates and to achieve an acceptable level of survival and rehabilitation in hemodialysis patients.^[6] As the toxic components of uremic toxins and their corresponding biological effects become increasingly clear, blood purification treatment that aims to remove these toxins has developed from a stage of life-sustaining to improving the quality of life and enabling the patients to return to society. Clinical applications of various models of extracorporeal blood purification technology show the clearance rates of middle and large molecule uremic toxins for these models take place in the following order: HD + hemoperfusion (HP) > HP > bio-artificial kidney > hemodiafiltration (HDF) > hemofiltration (HF) > HD.^[7, 8]

In this application, we outline an innovative research proposal to test the hypothesis that combination of hemoperfusion and hemodialysis treatment would be superior to regular hemodialysis treatment alone in maintenance hemodialysis (MHD) patients. We hope the result of this study will be an international reference to the optimized use of dialysis therapy in MHD patients.

Specific aim 1: The primary outcome of this study is to test if hemodialysis plus hemoperfusion treatment is superior to regular hemodialysis treatment alone in reducing all-cause mortality in MHD patients. The study will be conducted as a multi-center, open-label, randomized controlled trial in 1364 MHD patients, who will be randomly divided into 2 treatment groups: combination of hemoperfusion and hemodialysis treatment group and regular hemodialysis treatment group. The rate of all-cause mortality between 2 groups will be compared. *We hypothesize that patients receiving hemodialysis plus hemoperfusion treatment have lower rate of all-cause mortality than those receiving hemodialysis alone.*

Specific aim 2: The secondary outcome is to test if hemoperfusion combined with hemodialysis treatment is superior to regular hemodialysis treatment in terms of reducing cardiovascular-related mortality and major cardiovascular events (MACEs) as well as improving the quality of life. In the same proposed study outlined in **Specific aim 1**, the rate of cardiovascular-related mortality and MACEs as well as the quality of life will be compared between the 2 treatment groups. *We hypothesize that patients treated by combination of hemoperfusion and hemodialysis therapy will have lower rate of cardiovascular-related mortality and MACEs and have better quality of life than those receiving hemodialysis alone.*

RESEARCH DESIGN AND METODOLOGY

Study design: We propose to conduct a multi-center, open-label, randomized controlled trial in 1364 biopsy-proven MHD patients, who will be divided into 2 treatment groups (combination of hemoperfusion and hemodialysis treatment vs. regular hemodialysis treatment).

Ethics approval: The study protocol will be submitted to the ethics committees of all participating hospitals for final approval, and the study is in adherence with the Declaration of Helsinki.

Study duration: The duration of this study is composed of a 24-month observation period. The patient recruitment period should take 6-month. MHD patients who are eligible and have signed the informed consent will firstly enter a 1-month screening period. Patients who are eligible after the screening period will be randomized to 1 of the 2 intervention groups.

Inclusion criteria: Patients with the following criteria will be included in the study:

- 1) Age at 18-75 years old
- 2) Regular blood purification treatment at least 3 months before enrolled in this study
- 3) Standard Kt/V ≥ 1.2

Exclusion criteria: Patients with any of the following criteria will not be included in the study:

- 1) White blood cell count $< 4 \times 10^{9}/L$ and / or platelet count $< 100 \times 10^{9}/L$
- 2) Cerebral hemorrhage in the past 12 weeks
- 3) MACEs in the past 8 weeks
- 4) Severe heart failure (New York Heart Association [NYHA] class III or IV)^[9]
- 5) Active gastrointestinal bleeding, or coagulation dysfunction
- 6) Malignant tumor
- 7) Active infection
- 8) Pregnancy or lactation
- 9) Participating in clinical trials in the past 3 months
- 10) Mental disabilities

Treatment details:

Screening phase: All eligible patients will receive regular hemodialysis treatment for a screening period of 1 month.

A randomized, open-label, multi-centre trial comparing hemodialysis plus hemoperfusion versus hemodialysis alone in adult patients with end-stage renal disease (HD/HPvsHD)

Regular hemodialysis group: Patients randomized to this group will receive low-flux hemodialysis treatment at a frequency of 2 times a week and online-hemodiafiltration treatment at a frequency of once a week, with each treatment session lasting 4 hours.

Combination of hemoperfusion and hemodialysis treatment group: In this group, in addition to the treatments in regular hemodialysis group, hemoperfusion will be conducted once every two weeks using a HA130 resin hemoperfusion apparatus containing 130ml resin. During the treatment session, patients receiving hemodialysis and hemoperfusion for the first 2hrs using a HA130 resin hemoperfusion apparatus containing 130ml resin (Zhuhai Jafron Biomedical Co., Ltd, China) and the blood flow rate maintains between 150-200ml/min. After 2hrs when the hemoperfusion apparatus was depleted, the hemoperfusion cartridge will be removed and the blood went through the low-flux hemodialysis dialyzer alone for the rest 2hrs with the blood flow rate between 200-250ml/min.

Primary endpoints: All-cause mortality.

Secondary endpoints: Secondary endpoints include: 1) Cardiovascular-related mortality; 2) major cardiovascular events (MACEs); 2) Evaluation of quality of life.

Interim analysis: An interim analysis at month 12 will be performed by an independent data monitoring board to assess the risks and benefits of this study at time points prior to 24-month.

Statistical approach and power calculations:

Sample size calculation is based on the following assumptions: 1) α (2-sided) at 0.05; 1) 1- β at 80%; 3) 18% 24-month all-cause mortality in the control arm (subjects receiving hemodialysis and hemodiafiltration only)^[10, 11]; 4) a reduction of 24-month all-cause mortality by 30% (to 12.6%). Expecting a 15% attrition rate, a total of 682 patients per arm is needed, thus a total of 1364 patients will be needed in this trial.

For data analysis, categorical variables will be analyzed using the χ^2 or Fisher's exact test. Continuous variables will be analyzed using Student's *t*-test upon normal distribution, or the Mann-Whitney *U*-test otherwise. Primary outcomes will be analyzed using the Kaplan-Meier method followed by the log-rank test. Multivariate Cox regression will be used to analyzed factors that could influence all-cause mortality and CVD mortality after the adjustment for multiple relevant traditional and uremia-related risk factors for mortality. Data were analyzed on an intention-to-treat basis. All statistical analyses will be conducted using STATA (Version 14.0; Stata Corporation, College Station, Texas, US).

REFERENCES

A randomized, open-label, multi-centre trial comparing hemodialysis plus hemoperfusion versus hemodialysis alone in adult patients with end-stage renal disease (HD/HPvsHD)

6. Cambi V. Dialysis strategies. In: Davison AM, Cameron JS, Grünfeld JP, Kerr DN, Ritz E, Winearls CG, editors. Oxford Textbook of Clinical Nephrology. 3rd ed. Vol. 3. New York: Oxford University Press Inc; 2005. pp. 1899–908.

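### The protocol's only rule for a continuous outcome such as quality of life lets the observed distribution choose the test and makes no provision for a baseline score

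*Protocol*

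**What the plan says.** Specific aim 2 sets out to show superiority on cardiovascular mortality and MACEs "as well as improving the quality of life", with the hypothesis that patients on the combined treatment "have better quality of life than those receiving hemodialysis alone". The list of secondary endpoints gives only "Evaluation of quality of life". It names no instrument, time point, baseline measurement or analysed variable (follow-up score or change).

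Under Statistical approach and power calculations there is one rule for continuous data: "Continuous variables will be analyzed using Student's *t*-test upon normal distribution, or the Mann-Whitney *U*-test otherwise". Covariate adjustment appears once, for mortality: "Multivariate Cox regression will be used to analyzed factors that could influence all-cause mortality and CVD mortality". Quality of life is not part of that model.

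The Treatment details section places a month before randomisation: "All eligible patients will receive regular hemodialysis treatment for a screening period of 1 month". A baseline questionnaire could be given then, but the protocol does not say that one is.

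**The concern.** The rule is written for continuous variables in general. Applying it to quality of life is an inference, but the natural one, since no other stated method fits a continuous score.

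Read that way, it has two weaknesses.

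- **The data choose the test.** A t-test addresses a difference in means and a Mann-Whitney test addresses rank ordering. What the quality-of-life comparison estimates is therefore not fixed in advance. With several hundred patients per arm, a comparison of means does not need a normally distributed score, so the switch buys little.
- **The baseline score has no stated role.** A patient's score before randomisation usually predicts the later score. Using it as a covariate narrows the confidence interval at no cost in patients.

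At stake are the precision and interpretability of one of three secondary comparisons. The primary mortality analysis is not affected.

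**Working it through.** The protocol gives no effect size, SD or power for quality of life, so it has no figure of its own to reproduce here.

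**Inputs from the protocol**
- "α (2-sided) at 0.05"; 80% power (stated for mortality, borrowed here).
- 682 patients per arm, taken as given; 15% attrition.
- "18% 24-month all-cause mortality in the control arm", and 12.6% in the combined arm.

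**Assumptions**
- Correlation r between baseline and follow-up score: 0.3, 0.5 or 0.7.
- Equal SD at both times, set to 1.
- A difference of 0.15 SD, for illustration.

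**Step 1. Variance per patient under three analyses**
- Follow-up score alone: 1.
- Change from baseline: 2(1 − r).
- ANCOVA: 1 − r².

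ANCOVA relative to follow-up alone is 1 − r². Relative to change scores it is (1 − r²)/[2(1 − r)] = (1 + r)/2.

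| r | Follow-up alone | Change score | ANCOVA | Cut against follow-up alone | Cut against change score |
|---|---|---|---|---|---|
| 0.3 | 1 | 1.40 | 0.91 | 9% | 35% |
| 0.5 | 1 | 1.00 | 0.75 | 25% | 25% |
| 0.7 | 1 | 0.60 | 0.51 | 49% | 15% |

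These ratios do not depend on the number of patients.

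**Step 2. Patients with a score**
- 24-month survivors only: 682 × 0.82 = 559 and 682 × 0.874 = 596.
- If the 15% attrition is loss on top of death: 559 × 0.85 = 475 and 596 × 0.85 = 507.

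**Step 3. Detectable difference at 80% power**

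Formula: (1.960 + 0.842) × √[V × (1/n₁ + 1/n₂)], with V from Step 1.
- 559 and 596: √(1/559 + 1/596) = 0.0589. Unadjusted, 2.802 × 0.0589 = 0.165 SD. With ANCOVA, multiply by √0.91, √0.75 or √0.51: 0.157, 0.143 or 0.118 SD.
- 475 and 507: √(1/475 + 1/507) = 0.0639. Unadjusted 0.179 SD; ANCOVA 0.171, 0.155 or 0.128 SD.

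**Step 4. Power for 0.15 SD with 559 and 596 patients**

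Formula: Φ(0.15/(0.0589√V) − 1.96).

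| r | Follow-up alone | Change score | ANCOVA |
|---|---|---|---|
| 0.3 | 72% | 58% | 76% |
| 0.5 | 72% | 72% | 84% |
| 0.7 | 72% | 91% | 95% |

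**Step 5. Validity and choice of test**

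A simulation of 1500 runs used a mildly skewed bounded score (Beta(5,3), skew −0.31), with a Shapiro-Wilk test as the normality check. Type I error was 4–6% both for the t-test/Mann-Whitney rule and for ANCOVA with HC3 errors. Normality was rejected in at least one arm in every run, so the rule always led to Mann-Whitney. That last result depends on the chosen check and score; the protocol names no formal normality test.

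**The case against.** The strongest reply is that the protocol does not say the baseline score is ignored. A t-test or Mann-Whitney test on change from baseline fits the wording equally well, and an aim of improvement suggests such a change. This stands. A reader might infer that the plan discards baseline information and loses much of its power, from 95% to 72% at r = 0.7. The documents do not support that, because they give neither the analysed variable nor a correlation. With change scores at r = 0.7 power is already about 91%, and at r = 0.3 ANCOVA gains only four points over follow-up alone. What remains is that ANCOVA is the more precise under either reading for every positive correlation below 1.

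Other replies also have weight:
- Neither test is invalid, so no false-positive problem can be inferred.
- The normality check might be a plot or a judgement of skewness, so Mann-Whitney is not bound to be chosen. A Hodges-Lehmann shift could accompany it and give an estimate in score points. Even so, the protocol does not fix which quantity is reported.
- A statistical analysis plan that is not shown may specify an adjusted model. The point is nevertheless about a rule that this protocol states; a plan that followed it would inherit the weakness.
- ANCOVA among survivors still conditions on survival, which treatment is expected to change. This is correct, and the fix has to say so.

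**Conclusion.** The concern holds in limited form. The one rule stated for continuous outcomes lets the data choose between a mean and a rank comparison and makes no provision for a baseline quality-of-life score. One pre-specified baseline-adjusted model is better on both counts.

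The size of the gain depends on assumed correlations: 9% to 49% of variance against follow-up scores alone, and 35% to 15% against change scores, as r goes from 0.3 to 0.7. The absolute detectable differences also depend on how many patients provide a score, and the 559 and 596 leave out the stated attrition. The lack of a fixed estimate depends on no correlation. Type I error is not at issue.

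**What to change.** Under Statistical approach and power calculations, take quality of life out of the general rule and add text to this effect:

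*The quality-of-life score is compared between arms by a linear model (ANCOVA) with treatment and the pre-randomisation score as covariates and robust standard errors, whatever the distribution of the score. The adjusted mean difference and its 95% CI are reported. A Mann-Whitney test is a sensitivity analysis. The comparison is among patients alive and assessed; because mortality is expected to differ between arms, it does not describe all randomised patients, and baseline adjustment does not remove this selection.*

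State that the score is obtained in the screening month, before randomisation, and name the instrument and the follow-up time point to which the model applies. The t-test/Mann-Whitney rule can stay for descriptive comparisons.

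The cost is a few sentences and, if no baseline questionnaire is already given, one per patient in a month that the design already contains. No extra patients are needed. A baseline score not collected before randomisation cannot be recovered later, which matters in an open-label trial.

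### The primary log-rank test is valid but unadjusted; a Cox comparison using a few pre-randomisation predictors of death would probably add power cheaply

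*Protocol*

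**What the plan says.** All of this stands in the Protocol, under Statistical approach and power calculations, unless noted.

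- Primary analysis: "Primary outcomes will be analyzed using the Kaplan-Meier method followed by the log-rank test". No stratification factor or covariate is attached to that test.
- Adjusted model: "Multivariate Cox regression will be used to analyzed factors that could influence all-cause mortality and CVD mortality", with adjustment for several conventional and uraemia-specific predictors. These are not listed, their time of measurement is not given, and the text does not say whether treatment arm is in the model.
- Design assumptions: "α (2-sided) at 0.05", 80% power, "18% 24-month all-cause mortality in the control arm", and a 30% relative reduction, to 12.6%. Then "Expecting a 15% attrition rate", and the result: "a total of 682 patients per arm is needed, thus a total of 1364 patients will be needed in this trial".
- Follow-up (Study duration): "The duration of this study is composed of a 24-month observation period".
- Known before randomisation (Inclusion and Exclusion criteria): age within 18-75 years, at least 3 months of prior treatment, Kt/V of at least 1.2, and NYHA class not III or IV. A 1-month screening period precedes randomisation.

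**The concern.** In a survival comparison, leaving out strong baseline predictors of death costs power. The unadjusted hazard ratio then averages over patients with very different risks and lies closer to 1 than the ratio between patients of like risk. Adjustment also allows for chance imbalance in those predictors. An age range of 18 to 75 years makes at least one useful predictor of all-cause death plausible, and age must be known for every randomised patient.

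The trial has little power to spare. With no losses at all, its assumptions give about 209 deaths, which is what 80% power requires. Any loss to attrition takes power below that level. An analysis that recovers some of it without enrolling more patients is therefore worth having.

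The log-rank test gives a p-value but no effect estimate. The Cox sentence that follows it does not clearly commit to a treatment hazard ratio.

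**Working it through.** **Step 1. The plan's own figure.** Under exponential survival the implied hazard ratio is ln(1 − 0.126)/ln(1 − 0.18) = ln 0.874/ln 0.82 = 0.679.

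- Deaths needed (Schoenfeld): 4 × (1.960 + 0.842)² / (ln 0.679)² ≈ 209.
- Patients per arm: 209/(0.18 + 0.126) ≈ 684. The two-proportion formula gives 697.
- Deaths expected with 682 per arm and no losses: 682 × 0.306 = 208.7, for log-rank power of 80.0%.

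So 682 per arm is matched closely only when the 15% attrition is left out; with it, 684/0.85 gives 805. That is a separate matter. Here it only sets the starting power.

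**Step 2. Log-rank power after attrition.**

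- If 15% of patients contribute nothing: 682 × 0.85 ≈ 580 per arm, and 580 × 0.306 ≈ 177 deaths. Power = Φ(√(177.5/4) × 0.3877 − 1.960) = Φ(0.62) ≈ 73%.
- If losses are spread evenly over follow-up, so that about 7.5% of deaths are missed: 208.7 × 0.925 ≈ 193 deaths, and power about 77%.

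**Step 3. Effect of adjustment, by simulation.** Each patient has one standard normal prognostic score and an exponential survival time whose log-hazard rises by b per SD of the score. For each b the arm-specific hazards are solved so that 24-month mortality is 18% and 12.6%. Each simulated trial is tested by an unadjusted log-rank and by a Cox model with treatment and score, both two-sided at 5%. The documents do not give b, so it is an assumption shown over a range. There were 20,000 runs per setting at 580 per arm and 8,000 at 682 per arm.

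| b per SD | C-index (approx.) | 580 per arm: log-rank → adjusted Cox | 682 per arm: log-rank → adjusted Cox |
|---|---|---|---|
| 0 | – | 72.6% → 72.4% | not run |
| 0.5 | 0.65 | 72.5% → 74.2% | 78.6% → 80.4% |
| 0.8 | 0.70 | 72.8% → 77.9% | 79.2% → 83.9% |
| 1.0 | 0.73 | 72.2% → 80.3% | 79.9% → 86.4% |
| 1.3 | 0.80 | 73.8% → 86.7% | not run |

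Simulation error is about 0.3 points at 580 per arm (√(0.73 × 0.27/20,000)) and about 0.4 points at 682 (√(0.80 × 0.20/8,000)). The small differences down the log-rank columns are mostly of that order.

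**Step 4. Type I error.** With no treatment effect, b = 1.0 and 580 per arm, rejection rates were 5.0% for the log-rank and 4.7% for the adjusted Cox model. The power gain is not bought with false positives.

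**Step 5. What the gain consists of.** For the same mortality of 18% and 12.6%, the hazard ratio at a fixed score is 0.673, 0.662 and 0.651 at b = 0.5, 0.8 and 1.0, against 0.679 when the score is not prognostic. The adjusted model targets this somewhat stronger conditional effect.

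**The case against.** The strongest reply is that nothing here is an error. The log-rank test is valid for a randomised comparison of time to death, and it agrees with a sample size built on unadjusted mortality. It needs no choice of covariates, no handling of missing values and no conditional effect measure. The distance between the unadjusted and adjusted hazard ratios is a difference between marginal and conditional effects, not bias. All of this stands, and the point is therefore one of efficiency only.

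It may also be said that covariate lists belong in the SAP, which is not at hand. That is right about the list. But the protocol itself settles the primary test, and the point concerns that choice.

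Four stronger readings are tempting, and the documents do not support them.

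- A reader might infer that the trial collects a set of baseline risk factors and leaves it unused. The protocol has no schedule of baseline data. Only the eligibility items must be known before randomisation, and some are restricted by the criteria themselves: NYHA III and IV are excluded, and Kt/V is at least 1.2.
- A reader might infer that the Cox model will adjust for uraemic values measured after randomisation, on the pathway by which hemoperfusion is meant to work. The wording does not exclude this but does not say it either.
- A reader might infer that no adjusted treatment effect is planned. Treatment may well be one of the factors in the Cox model; the text leaves it open.
- A reader might take the largest simulated gains as what the trial would obtain. They assume a strong score, measured without error and correctly modelled. A few real variables in a population already narrowed by the exclusions may do less.

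**Conclusion.** The point holds as an inexpensive improvement to a valid analysis. Over the range shown, adjustment costs essentially nothing if the chosen variables turn out not to be prognostic (72.6% against 72.4%). It adds about 2 points of power at a C-index of 0.65, about 5 at 0.70 and 6 to 8 at 0.73. The gain of about 13 points at a C-index of 0.80 marks the upper end of the range and should not be planned on.

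These figures rest on the protocol's mortality assumptions, exponential survival and an assumed prognostic strength. The 580-per-arm figures also treat 15% of patients as contributing nothing; the 682-per-arm figures assume no losses. Missing covariates and stratification by centre were not simulated.

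**What to change.** Before the month-12 interim analysis, amend Statistical approach and power calculations as follows.

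1. Make the primary treatment comparison a Cox model with treatment and a short list of covariates named in advance: age first, then other prognostic values that the sponsor confirms are recorded before randomisation (Kt/V and NYHA class are candidates).
2. Report the adjusted hazard ratio with its 95% CI as the primary result.
3. Keep the Kaplan-Meier curves and the unadjusted log-rank test as a sensitivity analysis.
4. State that all covariates are limited to values measured before randomisation.
5. Give a simple rule for missing covariate values.

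Stratifying by centre is optional. The number of centres is not given, and very small centres would contribute little.

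The cost is mainly wording. The hazard ratio becomes conditional on the covariates and must be described so, a few missing baseline values need handling, and the sponsor must check which values are recorded before randomisation. No extra patients or visits are needed if the list is kept to such values.
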